8.7.2 Analysis of Secondary Efficacy Variables

All analysis on secondary efficacy variables will be performed using FAS.

The secondary efficacy endpoint is to evaluate the change in FPG from baseline to week 24 of MP-513 compared to Placebo. The same statistical methodology as described for primary analysis on primary efficacy endpoint will be used.

The line graph for mean change in FPG from baseline to Week 24 and Week 24 (LOCF) will be presented. The 95% CIs will also be shown in the graph with error bar. The plots of Week 24 and Week 24 (LOCF) will not be connected.

8.7.3 Analysis of Other Efficacy Variables

All other efficacy endpoint will be analysed using FAS. The other efficacy endpoints are as follows:

- Proportion of subjects who achieved HbA1c < 7.0% at Week 24
- Change in fasting insulin, C-peptide, and glucagon from baseline to Week 24
- Change in HOMA-IR and HOMA- β from baseline to Week 24
- Change in body weight from baseline to Week 24
- Change in HbA1c and FPG from baseline to Week 12

Proportion of subjects who achieved HbA1c < 7.0% at Week 24 (LOCF):

For the proportion of subjects who achieved HbA1c < 7.0% at Week 24 (LOCF), the comparison between treatments will be performed using logistic regression with treatment as fixed effect and baseline HbA1c value as a covariate. The subjects who have HbA1c < 7.0% at baseline will be excluded from the analysis.

The odds ratio (OR) with 95% Wald CIs will be presented for between treatment groups comparison of responder rate (i.e. proportion of subjects who achieved HbA1c < 7.0% at Week 24). The Wald Chi-Square p-value for significance of treatment effect after controlling for baseline HbA1c will also be displayed.

For logistic regression analysis, the dichotomous response variable will be coded as '1' (for subjects who achieved HbA1c < 7.0% at Week 24) and '0' for subjects for whom HbA1c \geq 7.0% at week 24.

The frequency count and percentage of subjects who achieved HbA1c < 7.0% at week 24 will also be summarized by treatment groups.

Other efficacy endpoints:

For the remaining other efficacy endpoints, namely;

- Change in fasting insulin, C-peptide, and glucagon from baseline to Week 24
- Change in HOMA-IR and HOMA- β from baseline to Week 24

- Change in body weight from baseline to Week 24
- Change in HbA1c and FPG from baseline to Week 12

The line graph for mean change in other efficacy endpoints from baseline to Week 24 and Week 24 (LOCF) will be presented. The 95% CIs will also be shown in the graph with error bar. The plots of Week 24 and Week 24 (LOCF) will not be connected.

The same statistical methodology as described for primary analysis on primary efficacy endpoint will be used.

8.7.4 Subgroup Analyses

The sub-group analysis will be performed for the primary efficacy endpoint i.e. Change in HbA1c from baseline to Week 24 for the subgroups mentioned in section 7.10.

Analyses of these subgroups will be performed using FAS. The analysis will be based on the same methods described for the primary analysis of primary efficacy endpoint.

8.8 Analysis of Safety

All safety data will be summarized by treatment groups using the Safety Analysis Set. No formal statistical test would be performed to determine statistical significance between treatment groups.

8.8.1 Adverse Events

All AE summary tables will include only TEAEs, unless otherwise specified.

Adverse events will be summarized by SOC and PT. A subject will only be counted once per SOC and PT within a treatment.

For AEs by severity grade (mild, moderate, severe), if a subject has multiple events occurring in the same SOC or same PT, then the event with the maximum intensity (i.e. severe) will be counted.

For AEs by relationship to study drug, if a subject has multiple events occurring in the same SOC or same PT, the event with the highest association (i.e. related) to study drug will be summarized.

Adverse events will be presented in Internationally Agreed Order at SOC level and within each SOC, in decreasing order of the incidences (in MP-513, then in Placebo) at the PT level.

An overall summary of adverse events will be presented and will include:

- Subjects with at least one TEAE
- Subjects with any severe TEAE
- Subjects with any serious TEAE
- Subjects with any ADRs

- Subjects with any serious ADRs
- Subjects with any treatment emergent cardiovascular events
- Subjects with any study drug related treatment emergent cardiovascular events
- Subjects with any TEAE resulting in death
- Subjects with any ADR resulting in death
- Subjects with any TEAE leading to drug discontinuation
- Subjects with any ADR leading to drug discontinuation
- Subjects with Hypoglycaemia
- Subjects with study drug related Hypoglycaemia

The following summary tables will be presented by SOC and PT:

- All TEAEs
- TEAEs by relationship to study drug
- TEAEs by severity grade
- Serious TEAEs
- Treatment emergent cardiovascular events
- Study drug related treatment emergent cardiovascular events
- All ADRs
- Serious ADRs
- TEAEs leading to drug discontinuation,
- ADRs leading to drug discontinuation

The following listings will be presented by subject:

- All AEs
- TEAEs
- Serious TEAEs
- TEAEs leading to drug discontinuation
- Treatment emergent cardiovascular events
- All ADRs
- All hypoglycaemic episodes

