6.3.3 Withdrawals and Replacement of Subjects

Subjects may be discontinued from study at any time. Subjects are also free to discontinue their participation in the study at any time without prejudice to further treatment.

In the eCRF, study completion or discontinuation will be documented with the reason for any discontinuation. Possible reasons for a subject discontinuing participation in the study are:

- AE(s) that endanger the health of subjects, making it ethically unacceptable to continue
- Deterioration of the subject's clinical condition(s) that requires appropriate therapy/treatment during the study period
- Withdrawal of consent
- Other cases where the investigator decides the study for the relevant subject should be discontinued.

Subjects' condition are clearly no longer suitable to continue in the study. The subjects with a lack of glycaemic control during the double-blind treatment period will be discontinued from the study and referred to appropriate anti-hyperglycaemic therapy. Inadequate FPG measured in the central laboratory is defined as follows:

- (1) FPG > 270 mg/dL (15 mmol/L) from baseline to Week 8 (inclusive).
- (2) FPG > 240 mg/dL (13.3 mmol/L) from Week 8 to Week 12 (inclusive).
- (3) FPG > 200 mg/dL (11.1 mmol/L) from Week 12 to Week 24 (exclusive).

In case of an AE, the subject should be followed up, whenever possible, until the subject recovers or until the investigator considers the situation to be no longer clinically significant. Subjects who discontinue prematurely from the study will not be replaced.

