Further details will be outlined in the eCRF manual.

Cardiovascular events

An Event Adjudication Committee (EAC) will be set up to evaluate the cardiovascular events.

Cardiovascular events are defined as below: Death; Myocardial Infarction; Hospitalisation for Unstable Angina; Stroke & Transient Ischaemic Attack (TIA) (fatal & non-fatal); Urgent Revascularisation Procedures; Hospitalisation for Heart Failure

The detailed review procedure will be developed in a booklet prior to initiating the trial.

Adverse Events

All AEs that occur during the study from the signing of informed consent form through to 14 days after the final dose of the study drug are to be collected and reported on the eCRF, regardless of whether they are reported by the subject, elicited by investigator questioning, detected through physical examination, or by other means.

As far as possible, each AE is described by:

- duration (start and end dates)
- severity grade (mild, moderate, severe)

- investigator causality assessment (relationship to the study product)
- action taken (change of study medication)
- outcome
- seriousness

Definitions and Handling of Adverse Events

AE

An AE is any untoward medical occurrence (change in anatomical, physiological, metabolic function, or clinically significant laboratory abnormality) in a subject, which does not necessarily have any causal relationship with the product under investigation.

SAE

An SAE is any untoward medical occurrence that at any dose:

- results in death
- is life-threatening (Note: the term “life-threatening” refers to an event in which the subject is at risk of death at the time of the event; it does not refer to an event which hypothetically may cause death if it is more severe)
- requires subject hospitalisation or prolongation of existing hospitalisation (for the purpose of this study, a hospitalisation is defined as a hospital stay of at least 8 hours and/or an overnight stay)
- results in persistent or significant disability/incapacity
- is a congenital anomaly/birth defect

or

- other medically important condition

Events that require intervention to prevent one or more of the outcomes listed in the definition above are also to be considered as serious. Examples of such events are intensive treatment in an emergency room or at home for allergic bronchospasm, blood dyscrasias or convulsion that does not result in hospitalisation, or development of drug dependency or drug abuse.

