4.5 Determination of Sample Size

The sample size was estimated based on the primary efficacy variable for assessing treatment difference in mean change in HbA1c from baseline at Week 24 between MP-513 and placebo. The data used for samples size calculation was based on the studies of MP-513 in Japan and other Dipeptidyl Peptidase-4 (DPP-4) inhibitors in China. For a two sided t-test of difference with 0.05 significance level and 90% power of test, 86 subjects per treatment group is required to detect a treatment difference of 0.5% in mean change in HbA1c from baseline at Week 24 with a common standard deviation of 1.0%.

Considering the drop-out rate of 30% and China Food and Drug Administration (CFDA) (on drug registration Code 28) requirement of at least 100 pairs of subjects to be enrolled in a phase 3 study, a total of 240 subjects (120 subjects per treatment group) are required to be randomized in this study.

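### Adverse events are summarised as crude percentages, while the FPG withdrawal rule is likely to shorten placebo observation; a person-time rate beside them would remove a modest bias against MP-513

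*SAP*

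**What the plan says.** SAP 7.1 summarises discrete variables by counts and percentages. SAP 8.8.1 applies this to adverse events: "A subject will only be counted once per SOC and PT within a treatment". Every row of the overall summary is a number of subjects with some kind of event. SAP 8.8 plans no formal safety test. The SAP narrative mentions no exposure-adjusted rate or time-to-first-event summary for safety. SAP section 12 holds the table shells, which were not in the supplied text.

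Three other provisions determine how long each subject is observed:

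- **Withdrawal.** Protocol 6.3.3: "The subjects with a lack of glycaemic control during the double-blind treatment period will be discontinued from the study". The FPG limit is 270 mg/dL up to Week 8, 240 up to Week 12 and 200 from Week 12 until before Week 24.
- **Collection.** Protocol 6.6.2.4 covers events from consent "through to 14 days after the final dose of the study drug are to be collected".
- **Expected losses.** SAP 4.5 sizes the trial with the words "Considering the drop-out rate of 30" per cent, not split by arm or reason. Protocol 6.3.3 says that leavers are not replaced.

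Exposure duration is summarised under SAP 8.6, and discontinuations with reasons by treatment group under SAP 8.1. SAP 6.6 runs exposure from randomization to Visit 6 or, for early withdrawals, to the date unused treatment is returned.

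**The concern.** A subject who leaves early has less time in which to have a first event, but still counts as a full subject in the denominator. That does no harm when both arms lose subjects alike. Here the rule that ends observation depends on FPG, the secondary efficacy endpoint, which MP-513 is expected to lower. Protocol 6.3.1 admits subjects with FPG just under 270 mg/dL, so someone who enters between 200 and 270 and does not improve will cross a limit later. If that happens more often on placebo, placebo time at risk is shorter because of the design.

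Safety is part of the trial's single objective. Protocol section 4 also reports an earlier combination study of this drug with adverse events in 61.2% versus 46.5% of subjects and adverse drug reactions in 11.7% versus 2.0%. A few spurious points in the same direction could be read as confirmation.

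**Working it through.** **The plan's own figure.** SAP 4.5 states no adverse event rate, so only its sample size can be reproduced. With difference 0.5, SD 1.0, two-sided 0.05 and 90% power, the normal approximation is 2 × (1.960 + 1.282)² × 1.0² / 0.5² = 84.06, or 85 per group. The exact t solution is 85.03, rounded up to the stated 86. Allowing for 30% loss, 86 / 0.70 = 122.9, close to the 120 per group randomized.

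**Inputs for the adverse event check**

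- From the documents: a completer is observed for 24 + 2 = 26 weeks, and a subject who stops at week w for w + 2 weeks.
- From Protocol section 4, as illustration: placebo incidence over 12 weeks of 46.5% (any adverse event) and 2.0% (adverse drug reactions) in the thiazolidinedione combination study.
- Assumed: the same constant hazard in both arms; withdrawals spread evenly over Weeks 12 to 24; the withdrawal shares in the table.

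**Formulas.** The hazard is h = −ln(1 − p)/12, giving 0.0521 per week for 46.5% and 0.00168 for 2.0%. A completer has an event with probability 1 − exp(−26h). For a withdrawn subject, averaging over 14 to 26 weeks of observation gives 1 − [exp(−14h) − exp(−26h)]/(12h). At h = 0.0521 these are 74.2% and 64.2%. Each arm's crude percentage is the mixture, so the false excess is the difference in withdrawal shares times about 10.0 points.

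| Withdrawn, placebo / MP-513 | MP-513 | Placebo | False excess |
|---|---|---|---|
| 10% / 2% | 74.0% | 73.2% | 0.8 |
| 20% / 5% | 73.7% | 72.2% | 1.5 |
| 30% / 0% | 74.2% | 71.2% | 3.0 |
| equal | – | – | 0 |

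For an event seen in 50% of subjects over 26 weeks, the same three rows give 0.7, 1.3 and 2.7 points. For the 2.0% event at 20% / 5%, the percentages are 4.2% and 4.1%, a ratio of 1.04. That matches the ratio of mean observation, 25.7 / 24.8 weeks.

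**Alternative split by all-cause drop-out.** If every leaver stops at Week 14 (16 weeks observed), the 50% event has probability 1 − 0.5^(16/26) = 34.7%. Each 10-point gap in drop-out then adds 0.10 × (50.0 − 34.7) = 1.5 points. A split of 35% / 25% gives 1.5; 40% / 20% gives 3.1.

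**Effect of person-time.** Observed for T weeks, a subject contributes 1 − exp(−hT) expected first events and [1 − exp(−hT)]/h expected weeks at risk. The ratio is h whatever T is, so both arms return the same rate. For the 50% event that is 0.02666 × 52 × 100 = 138.6 per 100 subject-years in each arm.

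**The case against.** The strongest reply is that the differential withdrawal is assumed. The 30% is an all-reason allowance, and no document gives withdrawal by arm. The nearest study in Protocol section 4, on metformin for 24 weeks, reports 88 placebo subjects in the double-blind period and 70 in the open-label period, so 18/88 = 20% did not continue; its withdrawal rules are not given. This stands: the size is conditional, and only the likely direction follows from the rule.

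A reader might infer a false excess of 5 to 10 points. That needs many placebo withdrawals by about Week 8, or drop-out as lopsided as 50% against 10%. The documents support neither. Up to Week 8 the limit is 270 mg/dL and entry already requires less than 270, so a subject who merely fails to improve is not removed then.

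A reader might also infer that a real difference could not be told apart from unequal follow-up, or that a false significant result could arise. Neither follows. Exposure, discontinuation reasons and subject listings are all planned, so an imbalance would show and rates could be worked out afterwards. No safety test is planned. What remains is that the adverse event tables themselves ignore the imbalance, and exposure as defined in SAP 6.6 omits the 14-day collection window, so it is not time at risk.

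The direction is not universal. Events linked to hyperglycaemia could go the other way, and early clustering of events would shrink the artefact.

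**Conclusion.** The point holds as a modest limitation of a descriptive comparison. If MP-513 lowers FPG, crude percentages for events unrelated to hyperglycaemia are likely to lean against it by about 1 to 3 points for a common event and a fraction of a point for a rare one. This assumes equal constant event rates, withdrawals mostly at Week 12 or later, and more placebo than MP-513 withdrawals. Subjects entering above 240 mg/dL could leave somewhat earlier. With equal withdrawal there is no bias. The absence of a person-time measure is established for the SAP narrative only. Severity is low.

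**What to change.** Keep the percentages. In the overall adverse event summary and the main SOC/PT tables (TEAEs, which by SAP 6.8.1.1 include hypoglycaemia; ADRs; cardiovascular events), add subjects with an event per 100 subject-years and show subject-years per group.

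Define time at risk from Day 1 to the first event or to the end of adverse event collection: 14 days after the last dose, or last contact if earlier. The supplied text does not confirm that a last-dose date is recorded. Where none is, use the SAP 6.6 exposure end date plus 14 days, still capped at last contact. Specify this before unblinding.

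The cost is a paragraph in the SAP and one more column in these tables. The tables become larger, and the rate assumes a roughly constant event rate. It does not correct for the selective removal of high-glucose subjects. The withdrawal rule, data collection and primary analysis are unchanged.

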8.8.2 Clinical Laboratory Evaluations

Laboratory results (hematology and blood chemistry) will be summarized by treatment groups using descriptive statistics for observed and change from baseline values for all the post baseline assessments visits. The categorical parameters from urinalysis will be summarized by frequency counts and percentages.

Additionally, shift tables will be produced. The shift tables will be based on the classification of laboratory results i.e. Low/Normal/High of post baseline visits compared to the grading of baseline results.

A full subject listing will be presented for laboratory results.

Serum pregnancy test results for female subjects will be listed.

8.8.3 Vital Signs

Vital signs (pulse rate, systolic and diastolic blood pressure, and body temperature) will be summarized by treatment groups using descriptive statistics for observed and change from baseline values for all the post baseline assessments visits.

A full subject listing will be presented for vital signs results.

8.8.4 Electrocardiogram (ECG)

ECG measurements (PR-interval (ms), RR-interval (ms), QRS-interval (ms), QT-interval (ms), QTc (ms) and heart rate (beats/min)) will be summarized by treatment groups using descriptive statistics for observed and change from baseline values for all the post baseline assessments visits. The investigator interpretation of ECG results (normal, abnormal not clinically significant and abnormal clinically significant) will be summarized by treatment groups using frequency counts and percentages.

A full subject listing will be presented for the ECG result and investigator interpretation.

8.8.5 Physical Findings

A full subject listing will be presented for the physical examination screening result.

9 COMPUTER SOFTWARE

All analyses will be performed by [REDACTED] using version 9.2 or later of SAS® software. All summary tables and data listings will be prepared by utilizing SAS® software. The standard operating procedures (SOPs) of [REDACTED] will be followed in the creation and quality control of all data displays and analyses.

11 APPENDICES

11.1 APPENDIX 1: STATISTICAL ANALYSIS AND PROGRAMMING DETAILS

11.1.1 Analysis of Covariance

This test will be used for testing whether population means of response variable (e.g. change in HbA1c from baseline to week 24) are equal across levels of treatment (MP-513 and Placebo) after controlling for the effect of continuous covariate i.e. baseline value and fixed effects i.e. treatment. Following code can be used for fitting ANCOVA model:

```
proc mixed data=mydata (where=(visit='Week 24'));
```

```
class trt;
model change = base trt/solution ddfm=kr;
lsmeans trt/diff=CONTROL('placebo') cl;
Ods output LSMeans = lsm (keep=trt estimate);
Ods output Diffslsm;
run;
```

Where,

- Response variable 'change' is the change from baseline to an endpoint visit
- trt is a categorical variable for treatment group (MP-513 or placebo)
- base is continuous baseline covariate
- Class statement specifies the classification variables.
- diff=CONTROL requests the differences with a control that, by default, is the first level of the specified LS-mean effect. Thus to specify which level is to be considered as control specify that in parentheses i.e. ('placebo').
- Dataset 'lsm' will contain the estimate for least square means (LS-means) for treatment groups under the variable 'estimate'.
- Dataset 'diffslsm' will contain estimate of difference of LS-means under variable 'estimate', standard error of LS-means difference under variable 'stderr', p value (using t test) for testing the significance of the difference between LS-means under variable 'probt' and the confidence limits for difference of LS-means under variable 'lower' and 'upper'.

11.1.2 Mixed Effects Model for Repeated Measure Analysis

This test will be used for testing whether population means of response variable (e.g. change in HbA1c from baseline to week 24) are equal across levels of treatment (MP-513 and Placebo) after controlling for the effect of continuous covariate i.e. baseline value and fixed effects i.e. treatment, visit and interaction of treatment and visit. Following code can be used for MMRM analysis:

```
proc mixed data=mydata;
class subid trt visit;
model change = base trt visit trt*visit / solution ddfm=kr;
repeated visit/ subject=subid type=un;
lsmeans trt*visit/cl diff;
ods output LSMeans = lsm(keep=trt visit estimate where=(trt='MP-513' and
visit='Week 24'));
ods output Diffslsm=diffslsm(keep=trt visit _trt _visit estimate stderr
probt lower upper where=(trt='MP-513' & _trt='Placebo'
& visit='Week 24' & _visit='Week 24'));
run;
```

Where,

- Response variable 'change' is the change from baseline to different visits.
- Class statement specifies the classification variables.
- trt is a categorical variable for treatment group (MP-513 or placebo)
- base is continuous baseline covariate
- Ddfm=kr specifies 'Kenwardroger' method of computing denominator degree of freedom for the tests of fixed effects.

- *Type= un specifies the within- subject variance covariance matrix as ‘unstructured variance covariance matrix’.*
- *Dataset ‘lsm’ will contain the estimate for least square means (LS-means) for treatment groups at week 24 under the variable ‘estimate’.*
- *Dataset ‘difflsm’ will contain estimate of difference of LS- means under variable ‘estimate’, standard error of LS-means difference under variable ‘stderr’, p value (using t test) for testing the significance of the difference between LS-means under variable ‘probt’ and the confidence limits for difference of LS-means under variables ‘lower’ and ‘upper’.*

11.1.3 Logistic Regression

The response variable will be dichotomous with values ‘Y’ (representing the event of interest, ex. subjects achieving HbA1c<7.0%) and ‘N’. For the categorical fixed effect, i.e. variable ‘treatment’, the lower value of the coded variable will be used as the denominator of the ratio. So if treatment is coded as: 1=’MP-513’, 2=’Placebo’ then option ref=last in the ‘class’ statement will specify the reference level as 2 i.e. 1 vs 2.

The following code can be used for logistic regression model:

```
proc logistic data=mydata;
  class treatment/ref=last;
  model response (event='Y')=base treatment;
  ods output
    ParameterEstimates= pval (where= (variable='Treatment'))
    OddsRatios=oddr;
run;
```

Where,

- *Class statement specifies the classification variables.*
- *base is continuous baseline covariate.*
- *Dataset pval will contain the p value for wald chi square test (under variable ‘ProbChiSq’) for testing the significance of treatment effect.*
- *Data oddr will contain odds ratio (under variable ‘OddsRatioEst’) and 95% Wald confidence limits for odds ratio (under variables ‘LowerCL’ and ‘UpperCL’) for between treatment comparison of responder rate*
